3.1.5.2 AST/ALT < 2-times normal and a total bilirubin < 2.0 mg/dL

3.1.5.3 Serum creatinine < 2.0 mg/dl or a creatinine clearance of ≥ 60 ml/minute

3.1.6 Subjects with one or more of the following cardiac risk factors must complete a stress radionuclide scan with no evidence of myocardial ischemia or heart failure: (a) a history of cardiac disease, (b) age greater than 65 years old, (c) any clinically significant abnormality found on ECG (required at baseline), or (d) significant risk factors for coronary artery disease (history of significant dyslipidemia; any treatment for dyslipidemia; or two first degree relatives with a documented myocardial infarction prior to age 55).

3.1.7 Subjects with significant history of pulmonary disease, shortness of breath at rest, or known COPD must have pulmonary function tests within 35% of normal age-predicted values.

3.1.8 Subjects must be willing and able to provide informed written consent prior to any study-related procedures.

3.1.9 Subjects must have no immediate requirements for palliative chemotherapy, palliative radiotherapy, or palliative hormonal therapy.

3.1.10 Subjects must be willing and able to discontinue antihypertensive medications if advised to do so for days of hu14.18-IL2 infusion.

3.1.11 Subjects must have slides available from stage III or stage IV melanoma. Paraffin blocks are preferable, but at a minimum, slides documenting melanoma by biopsy (including fine needle cytology) must be available for pathology review, and potential restaining/staining (see Section 7.4, Surgical Pathology Guidelines). Prior histologic demonstration of metastatic melanoma (either stage III or Stage IV) may be utilized if a repeat biopsy is not clinically needed to establish eligibility.

3.2 Exclusion criteria

- 3.2.1** Subjects are ineligible if they have received mAbs during biologic therapy, tumor imaging, purging of autologous marrow/stem cells for re-infusion or for any other reason unless serological testing is performed. If the absence of detectable antibody (over background) to hu14.18 is documented, the subject is eligible for the study.
- 3.2.2** Subjects treated with IL2 in the past that developed intolerable (Grade 4) IL2-related side effects.
- 3.2.3** Subjects who have received any (standard or experimental) systemic therapy for stage IV disease.
- 3.2.4** Women of childbearing potential will be excluded if they are pregnant, nursing, or not using effective contraception during the treatment period.
- 3.2.5** Subjects with symptoms of ischemic cardiac disease, congestive heart failure, myocardial infarct within the immediate preceding 6 months and/or uncontrolled cardiac rhythm disturbance.
- 3.2.6** Subjects with significant psychiatric disabilities or seizure disorders.
- 3.2.7** Subjects who have had major surgery within the past 3 weeks.
- 3.2.8** Subjects with clinically detectable pleural effusions or ascites.
- 3.2.9** Subjects with organ allografts.
- 3.2.10** Subjects who require or are likely to require corticosteroid or other immunosuppressive drugs or have used them within 2 weeks of registration.
- 3.2.11** Subjects with significant intercurrent illnesses.
- 3.2.12** Subjects with active infections or active peptic ulcer unless these conditions are corrected or controlled.
- 3.2.14** Brain metastases, whether active or inactive. A head MRI or head CT scan will be required at baseline to rule out silent metastases.
- 3.2.15** Active second malignancy other than non-melanoma skin cancer. Patients will be considered eligible if they have been continuously disease free for ≥ 5 years prior to the time of enrollment.
- 3.2.16** Infection with human immunodeficiency virus (HIV), hepatitis B surface antigen (HBs Ag) carrier state or with clinical evidence of hepatitis. Treatment may be initiated before laboratory confirmation of HIV and HBs Ag negativity, but will be stopped if results are positive.
- 3.2.17** Subjects with a clinically significant neurologic deficit or objective peripheral neuropathy (Grade ≥ 2) are ineligible.
- 3.2.18** Known hypersensitivity to the study drug, Tween-80® or to human immunoglobulin.

3.2.19 Patients with a known history of diabetes mellitus that has required systemic therapy within the past 3 months (either oral hypoglycemic agents or insulin) will be excluded, as treatment with hu14.18-IL2 may alter blood glucose levels.

3.2.20 Legal incapacity or limited legal capacity.

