1.5.4.4 Surgical resection randomization –Before versus After Course 1 therapy

All subjects will be followed for time to recurrence and overall survival measured from the completion of their second course of treatment. Subjects in all study groups will have spent equivalent time since study entry in getting to this point: all will have had their surgical resection and their first 2 courses of study treatment. The differences will be in the timing of their resection (pretreatment in Group B and after Course 1 in Group A). While Group A subjects also will be providing informative data regarding the influence of one course of hu14.18-IL2 on the histopathology of the resected tumor, Group B will be providing essential histopathology control data. Furthermore, any future use of this approach for patients that can achieve MRD surgically (i.e., a Phase III trial that might be based on data from this study), would be anticipated to utilize the treatment schedule for Group B, as it would allow administration of the optimal therapy (whichever this pilot trial suggests that to be) to patients that can achieve a CR prior to receiving all courses of therapy. Thus obtaining clinical and lab data from all study groups is important. Even though the numbers are small, and there will be much variability in assays and subject characteristics, it makes sense for these treatment groups to be treated at the same time (rather than sequentially), and with an effort made to keep both groups comparable in characteristics and assessments. Thus, subjects entered into this study, following confirmation of meeting all eligibility criteria and obtaining signed informed consent, will be randomized to either of the treatment groups. The randomization will stratify subjects for the single variable of “extent of surgery required”. Namely, subjects needing a thoracotomy, a laparotomy, or deep soft tissue excisions in 3 anatomic locations would be considered to need “extensive resection”, while those subjects requiring only superficial cutaneous excisions or deep soft tissue excision in only 1 or 2 locations would be considered to need “non-extensive resection”. Randomization will be performed for all subjects entered into the study, in order to keep all treatment groups comparable to each other with respect to the number of subjects requiring extensive versus non-extensive resection.

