5.2 Surgical resection of all detectable melanoma

5.2.1 Treatment Group A

Subjects in Group A will have complete surgical resection of all detectable melanoma following Course 1 of hu14.18-IL2. Surgical resection will be scheduled for 7-14 days following the completion of the first 3-day course of therapy (i.e., days 10-17) in order to insure reversal of hu14.18-IL2 toxicities prior to the surgery. These ranges will allow enough flexibility so that the appropriate surgical subspecialist will be available to perform the resection.

Once the subject has recovered from the surgery (2-4 weeks, depending upon the nature of surgery (Section 4.4.8), the subject will begin Course 2 of treatment. Decisions regarding whether a subject has recovered sufficiently from surgery to begin Course 2 of treatment will be left to the discretion of the treating physician(s). To aid in this decision, laboratory tests may be ordered as warranted clinically, but no specific tests are required for this assessment. Subjects undergoing “extensive surgery” (see Section 4.4.8) will not begin Course 2 of study treatment until at least 21 days after surgery. Subjects undergoing “non-extensive surgery” will not begin Course 2 of study treatment until at least 14 days after surgery (see Section 4.4.8). No course of hu14.18-IL2 therapy will be administered sooner than 4 weeks after day 1 of the prior course of hu14.18-IL2 therapy. Subjects will receive a total of 3 courses of treatment as described in Section 5.3.

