5.2.2 Treatment Group B

Subjects in Group B will have complete surgical resection of all detectable melanoma upon study entry, prior to Course 1 of hu14.18-IL2. Once the subject has recovered from the surgery (2-4 weeks, depending upon the nature of surgery (Section 4.4.8), the subject will begin Course 1 of treatment. Decisions regarding whether a subject has recovered sufficiently from surgery to begin Course 1 of treatment will be left to the discretion of the treating physician(s). To aid in this decision, laboratory tests may be ordered as warranted clinically, but no specific tests are required for this assessment. Subjects undergoing “extensive surgery” (see Section 4.4.8) will not begin Course 1 of study treatment until at least 21 days after surgery. Subjects undergoing “non-extensive surgery” will not begin Course 1 of study treatment until at least 14 days after surgery (see Section 4.4.8). No course of hu14.18-IL2 therapy will be administered sooner than 4 weeks after day 1 of the prior course of hu14.18-IL2 therapy. Subjects will receive a total of 3 courses of treatment as described in Section 5.3.

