7.0 STUDY PARAMETERS

7.1 Guidelines

7.1.1 All CT and MRI scans should be done within 3 weeks prior to registration. (**NOTE:** No study specific procedures should be done prior to subject’s inclusion in study and obtaining Informed Consent.) All areas identified as malignant disease, or suspicious for malignant disease, must be resectable. The surgical resection must remove these sites, as confirmed by the surgeon.

7.1.2 CBC with differential, platelets (plts), AST, ALT, alkaline phosphatase, bilirubin, albumin, LDH, Na, K, glu, phos, Mg, Ca, Cr, BUN, HgbA1C, C-reactive protein (CRP), TSH, INR, PTT, urinalysis, HIV, and HBsAg should be done ≤ 2 weeks before randomization and meet eligibility criteria.

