7.2 Clinical Assessment

The detailed schedules for treatment administration and clinical monitoring are included below in Tables 5, 6A, and 6B.

TABLE 5. CLINICAL ASSESSMENT FOR EACH TREATMENT COURSE

DAY	Base Line ²	Week 1						Weeks 2-4	Week 5 ¹
		1	2	3	4			8	29/1 ¹
Hu14.18-IL2		X	X	X					X
Complete history/PE	X								
Physical Exam		X	X	X					X ³
Adverse event assessment		X	X	X	X			X	X ³
Weight	X	X	X	X	X			X	X ³
Performance Status	X	X	X	X	X			X	X ³
Pregnancy Status	X								
ECG	X								
Tumor Assessment	X ⁶								X ⁴
Vital signs (T, BP, P, RR)	X	X ^{5,6}	X ^{5,6}	X ^{5,6}	X			X	X ³
CBC, diff, plts	X			X				X	X ³
AST, ALT, T bili, alk phos, alb, LDH, Na, K, Ca, Mg, Cr, BUN, CRP ⁷	X			X				X	X ³
Serum phosphate ⁸ and glucose ⁹	X			X				X	X ³
INR/PTT	X			X					X ³
Urinalysis	X								X ³
Hgb A1C, TSH	X								
HIV/HBsAg	X								
Head MRI or Head CT	X								
Biopsy	X ¹⁰								

¹ Day 29 of each course (+/- 7 days leeway to facilitate clinical scheduling) = day 1 of subsequent course.

² Baseline tests/exams, with the exception of laboratory assessments, may be performed on or before day 1 but must be performed ≤ 3 weeks prior to randomization. Laboratory assessments must be done ≤ 2 weeks prior to randomization.

³ These tests may be performed up to 1 week prior to initiating the next course of therapy, or day 22-29 of the present course if no more study therapy is to be administered.

⁴ Tumor assessments will take place at baseline and after Course 2. (Long-term follow-up will include further tumor measurements; see Table 8.) The assessment after Course 2 will be performed no earlier than day 8, but can be performed out to day 29 (+/- 7 days leeway to facilitate clinical scheduling), thus allowing adequate time to obtain biopsies of any questionably recurrent disease to determine if the subject is eligible to continue on study (see Section 5.3.1.3 for details regarding these biopsies). Baseline radiological evaluation will include CT scans of the chest, abdomen, and pelvis, and head MRI. Assessments after Course 2 and during long-term follow-up will include CT scans of areas of known prior disease. Other examinations can be performed as warranted clinically. Consistency will be maintained in the imaging modality used to measure tumor while patient is on study.

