8.1.2.8 Administration of hu14.18-IL2

The subject's height and weight determination at the baseline prestudy evaluation (≤ 7 days before starting the first cycle of treatment) will be used to calculate the body surface area (BSA) for treatment cycle one. Calculation of the body surface area will be repeated prior to each subsequent treatment cycle (≤ 7 days before starting each subsequent treatment cycle)

The BSA determination will be multiplied by the dose (mg/m^2) to determine the subject's daily dose of hu14.18-IL2. The actual dosage of hu14.18-IL2 administered will be documented in the dispensing document in the subject file by the Investigator/Designee.

The dose of hu14.18-IL2 will be infused intravenously over 4 hours. Hu14.18-IL2 should be administered via a peripheral or central IV catheter and an 18 to 20-gauge needle. In-line filters must not be used when administering the diluted solution. Prior to and following each dose, the IV catheter should be flushed with 0.9% Sodium Chloride Injection.

Subjects will be treated in the hospital for the duration of infusions (Days 1 through 3 of each cycle) through the safety monitoring period, after which they will be released from the hospital. Subjects will be under close observation by the Investigator/physician or a designated skilled staff member during the infusion of hu14.18-IL2. Vital signs will be evaluated during infusion. (See Clinical Assessment [Table 5] for details.)

The Investigator will use clinical judgment, depending on the subject's status, in releasing the subject from close monitoring.

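### Section 3.2.16 lets hu14.18-IL2 start while HIV and HBsAg results are pending, with no deadline for the result, so a drug-first subject whom the protocol excludes could be dosed

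*Combined protocol and SAP*

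**What the plan says.** Section 3.2.16 makes HIV infection and the HBsAg carrier state exclusions. The same item then allows dosing before either is ruled out: "Treatment may be initiated before laboratory confirmation of HIV and HBs Ag negativity, but will be stopped if results are positive". It does not say when the result must be back.

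Four other places bear on the timing:

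- Section 7.1.2 lists HIV and HBsAg among the laboratory tests that should be done no more than 2 "weeks before randomization and meet eligibility criteria".
- Table 5 in Section 7.2 lists HIV/HBsAg at baseline, and its footnote 2 adds: "Laboratory assessments must be done ≤ 2 weeks prior to randomization".
- Section 1.5.4.4 says that subjects entered, "following confirmation of meeting all eligibility criteria and obtaining signed informed consent, will be randomized to either of the treatment groups".
- Section 4.3 requires every Section 3.0 requirement to be met, and Section 4.1 bars treatment before registration.

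The two groups reach their first dose differently. Under Section 5.2.2 a surgery-first subject with a non-extensive resection "will not begin Course 1 of study treatment until at least 14 days after surgery"; for an extensive resection the minimum is 21 days. For the drug-first group no minimum interval from randomization to Day 1 is stated. Group labels here follow the Schema and Section 5, where drug-first is Group A. Section 9 swaps the labels.

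**The concern.** The sponsor has decided that HIV-infected subjects and HBsAg carriers should not be in this trial, and the test that identifies them is already ordered before randomization. The allowance nevertheless lets a subject receive an IL2-based agent before the result is read. Stopping treatment afterwards limits further exposure but does not undo what has been given. Section 5.5.1 does not list a positive serology among its specific reasons for ending protocol therapy.

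The documents offer no reason for haste. Section 3.1.9 points the other way as far as it goes: "Subjects must have no immediate requirements for palliative chemotherapy, palliative radiotherapy, or palliative hormonal therapy". The same exclusion list handles another serology more strictly. Under Section 3.2.1, a subject with prior monoclonal antibody exposure becomes eligible only once absence of antibody to hu14.18 is documented.

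What is at stake is avoidable exposure of an excluded subject, and uncertainty for site staff about which rule governs. Nothing material changes in the power, the endpoints or the stopping rules.

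**Working it through.** The plan gives no figure on this point, so there is none to reproduce. The check has three parts.

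**1. Infusions already given when a positive result arrives (drug-first).** Inputs: infusions on days 1, 2 and 3 of each course and 3 courses (Section 5.3), so 3 × 3 = 9 planned; Course 2 no sooner than 4 weeks after Day 1 (Section 5.2.1), so day 29 at the earliest.

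| Positive result known | Infusions already given |
|---|---|
| before dosing on day 1 | 0 |
| before dosing on day 2 | 1 |
| before dosing on day 3 | 2 |
| after the day 3 dose, before dosing on day 29 | 3 |
| before dosing on day 30 | 4 |
| before dosing on day 31 | 5 |
| after the day 31 dose, before Course 3 | 6 |

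Three is therefore the most for any result that returns before Course 2. It follows from the calendar and an assumed turnaround; the protocol sets no such cap.

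**2. Chance that at least one excluded drug-first subject is dosed.** Inputs: 10 subjects in the arm (Section 9.3.2, up to 20 in total); p = probability of a positive test (assumed, 0.1% to 1%); f = share of drug-first subjects dosed with results pending (assumed, 25% to 100%). Neither p nor f is in the documents.

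P = 1 − (1 − p·f)^10

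| p | f = 0.25 | f = 0.5 | f = 1 |
|---|---|---|---|
| 0.001 | 0.0025 | 0.0050 | 0.0100 |
| 0.005 | 0.0124 | 0.0247 | 0.0489 |
| 0.01 | 0.0247 | 0.0489 | 0.0956 |

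If a negative result is required before the first dose, f = 0 and P = 0.

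**3. Delay caused by waiting.** Let T be the turnaround (assumed, 1 to 7 days), k the days from blood draw to randomization (0 to 14 under Section 7.1.2), and g the days from randomization to Day 1.

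Delay = max(0, T − k − g)

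Drug-first, worst case g = 0:

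| T (days) | k = 0 | k = 3 | k = 7 |
|---|---|---|---|
| 7 | 7 | 4 | 0 |
| 3 | 3 | 0 | 0 |
| 1 | 1 | 0 | 0 |

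Surgery-first: g is at least 14 (non-extensive) or 21 (extensive), so the delay is 0 for any T up to 14 days. For the same reason, the current allowance has no practical effect in that group unless the turnaround is longer than that.

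**Subjects to replace.** Expected positives among 20 = 20p = 0.02 to 0.2. They need replacing under the current wording too, because treatment stops before the 2 courses that Section 5.1 requires, unless the result is so late that both have been given.

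**The case against.** The best defence is that the allowance is deliberate. It stands in the same item as the exclusion and carries its own safeguard. Sections 1.5.4.4, 4.3 and 7.1.2 all refer to eligibility criteria, and 3.2.16, exception included, is one of those criteria. On that reading a specific exception sits inside a general rule. If the general sections override it instead, nobody excluded is dosed. This stands in part. A reader might infer a flat contradiction, and the documents do not support that. They show a tension and no statement of which rule governs.

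A reader might also infer that carriers or HIV-infected subjects would be harmed. The documents do not show it. Section 1.3.5 reports no Grade 4 toxicity in 33 Phase I subjects, and its Table 3 shows no Grade 3 AST or bilirubin at 6.0 mg/m². Section 10.2.2 says liver test rises are routine and usually settle within 2 to 3 days, and it stops the agent for Grade 3 hepatic toxicity. Clinical evidence of hepatitis remains an exclusion outside the allowance, Section 3.1.5.2 sets liver test limits at entry, and Table 5 repeats liver tests on days 3 and 8. The residual exposure is mainly clinically silent infection. This objection stands in full and keeps the point minor.

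Finally, Section 3.1.9 concerns palliative therapy only and says nothing about how soon a drug-first subject should reach surgery. That is fair: the documents give no reason for urgency, but 3.1.9 alone does not prove there is none.

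**Conclusion.** The point holds as a minor patient-safety improvement. Followed as written, Section 3.2.16 permits dosing a subject whom the protocol excludes, when waiting for a test already ordered would prevent it. The exposure falls in practice on the drug-first group: 0 to 3 infusions per affected subject if the result returns before Course 2, and more if it returns later. The chance that it happens at all is small, 0.25% to 9.6% across the arm. Every input to that range except the 10 subjects is assumed, and the top end needs 1% positivity with all 10 dosed while results are pending. No stronger claim, of documented harm or of damage to the trial's inference, is supported.

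**What to change.** Replace the second sentence of Section 3.2.16 with: *Negative HIV and HBsAg results must be on file before randomization where available, consistent with 7.1.2, and in every case before the first dose of hu14.18-IL2.* This states which rule governs and leaves the sampling window in Section 7.1.2 unchanged. A randomized subject who then tests positive is not dosed and is replaced under Section 5.1. Requiring the result before randomization without exception would also remove the exposure, but it could hold up surgery in the surgery-first group for no dosing reason.

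The cost is small. No test or visit is added. Drug-first Day 1 may slip by at most the turnaround, and not at all if blood is drawn early enough in the existing window. Surgery slips with it, because under Section 5.2.1 "Surgical resection will be scheduled for 7-14 days following the completion of the first 3-day course of therapy". The imaging and laboratory windows run back from registration and randomization, so a wait after randomization cannot breach them. Height and weight for the dose calculation must be taken no more than "7 days before starting the first cycle of treatment" (Section 8.1.2.8) and may need repeating.

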3.2.21 Bone metastases

4.0 REGISTRATION PROCEDURE

4.1 Subjects must not start protocol treatment prior to registration.

4.2 Subjects will be registered directly into Oncore by the Melanoma Research Staff

4.3 Subjects must meet all of the eligibility requirements listed in Section 3.0.

4.4 The following information will be requested during registration:

4.4.1 Protocol number

4.4.2 Investigator's name

4.4.3 Subject's name and medical record number

4.4.4 Subject demographics

4.4.5 Gender

4.4.6 Birthday (MM/DD/YYYY)

4.4.7 Race (according to the NCI classification)

4.4.8 Will complete surgical resection be “extensive” (i.e., require thoracotomy, laparotomy or excision of deep soft tissue metastases in 3 anatomic locations) or “non-extensive” (i.e., not require thoracotomy, laparotomy or excision of deep soft tissue metastases in 3 anatomic locations, but require only cutaneous/subcutaneous excisions and/or excision of deep soft tissue disease in only 1 or 2 locations)?

4.5 Subjects then will be randomized to one of the two study groups. (See Section 9.3.1 for more details on randomization process.)

